10.1 Subject Discontinuation

Frequency counts will be tabulated by treatment and total for the number of subjects who were dosed, the number of subjects who completed, and the number of subjects who discontinued early, along with the reason for discontinuation. Individual patient's treatment along with their study completion status and date will be provided in a listing.

10.2 Demographics

Descriptive statistics (N, mean, SD, minimum, median, and maximum) will be calculated for continuous demographic variables (age, weight, height, and body mass index [BMI]) and frequency counts will be tabulated for categorical demographic variables (gender, race, and ethnicity) by treatment and total.

10.3 Exposure to Study Drug

For each treatment, exposure to study drug will be summarized through frequency count (number of patients) and percentage by AM/PM of each study day for each scheduled dose.

10.4 Adverse Events

Adverse events will be coded with MedDRA dictionary version 18.0.

A treatment-emergent adverse event (TEAE) is defined as an AE that is starting or worsening at the time of or after study drug administration. All AEs collected by the clinics and recorded in the CRF are captured in the database and will be listed in by-patient data listings. Only TEAEs will be summarized in the report. Data will be summarized by SOC and preferred term.

Summary tables will include the number and the percentage of patients reporting the TEAE and percentage of patients dosed, the number of TEAEs and the percentage of total TEAEs. These results will be summarized by treatment and total. The number of patients reporting each TEAE and number of TEAEs will also be summarized by treatment, severity, and relationship to treatment.

A by-patient AE data listing, including verbatim term, preferred term, treatment, severity, outcome, and relationship to treatment, will be provided.

10.5 Clinical Laboratory Tests (Serum Chemistry, Hematology, Urinalysis)

Clinical laboratory assessments (serum chemistry, hematology, and urinalysis) will be performed at screening, Check-in, Day 29 (± 2), and Day 55 or Day 56 or early termination.

Descriptive statistics (N, mean, SD, median, minimum, and maximum) will be reported for numeric clinical laboratory results and change-from-baseline values by treatment and time point of collection. Baseline value will be the Check-in value and is the last non-missing measurement prior to dosing. Postdose recheck values will not be used for calculation of descriptive statistics. Shift tables describing out-of-range shifts from baseline (in frequency counts) will be created. Out-of-normal-range and clinically significant laboratory values will be listed by patient. Early termination record will be excluded from the summary. All laboratory results will be listed in by-patient data listings. Because clinical laboratory test results will come from multiple sites with different reference ranges, out-of-range tables and shift tables will still use original units for presentation. For mean and mean change summary tables, the results and ranges will be converted to SI units for presentation. In the lab listings, both original units and SI units will be presented.

10.6 Vital Signs and Pulse Oximetry

Vital signs include systolic and diastolic blood pressure, pulse rate, respiratory rate, and body temperature. They will be measured at screening, Check-in, predose and 1, 2, 6 hours postdose of Day 1, Days 15 (± 2), 29 (± 2), 43 (± 2), and predose and 1, 2, 6, 12 hours postdose of Day 55 or Day 56 or early termination. Pulse oximetry will be measured at screening, Check-in, and Day 55 or Day 56 or early termination. All vital signs and pulse oximetry results will be presented in a by-patient listing.

Descriptive statistics (N, mean, SD, median, minimum, and maximum) will be provided for vital sign variables and change from baseline at each assessment time point by treatment. Baseline value will be the Day 1 predose value and is the last observation, including rechecks, obtained prior to dosing. For pulse oximetry, baseline value will be the Check-in value and is the last observation, including rechecks, obtained prior to dosing. For the purposes of summary statistics calculations, recheck values will not be used in the determination of postdose values. Early termination record will be excluded from the summary.

10.7 12-lead Electrocardiogram

Twelve-lead ECGs will be performed at screening, Check-in, Day 29 (± 2), and Day 55 or Day 56 or early termination. All ECG results will be presented in a by-patient data listing.

Descriptive statistics (N, mean, SD, median, minimum, and maximum) will be provided for ECG variables (HR, PR, QRS, QT, and QTcB [Bazett's correction]) and

change from baseline at each assessment time point by treatment. Baseline value will be the Check-in value and is the last observation, including rechecks, obtained prior to dosing. For the purposes of summary statistics calculations, recheck values will not be used in the determination of postdose values. ECG results will also be classified as normal, abnormal, not clinically significant (ANCS), and abnormal, clinically significant (ACS). A normal-abnormal shift table will be created to describe shifts from predose baseline for postdose time points. Early termination record will be excluded from the summary.

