2. OBJECTIVES AND ENDPOINTS

2.1 Objectives

Primary Objective: To assess the safety and tolerability of two multiple oral YPL-001 dose levels versus placebo in moderate to severe chronic obstructive pulmonary disease (COPD) patients.

Secondary Objective: To assess the number and magnitude of daily respiratory symptoms of two multiple oral YPL-001 dose levels versus placebo in moderate to severe COPD patients.

Exploratory Objectives: To evaluate the following in moderate to severe COPD patients:

1. To assess BAL epithelial brushings for YPL-001 component levels.
2. To compare BAL samples for total cell count (cells/mL) macrophages, lymphocytes, neutrophils, and eosinophils as a percentage of total cells; neutrophil, macrophage, lymphocyte, and eosinophil counts as absolute inflammatory cell numbers in YPL-001 groups versus placebo group.
3. To compare BAL samples for TNF- α , IL-1 β , IL-4, IL-5, IL-6, IL-8, IL-13, MPO, neutrophil elastase, MCP-1, and MMP-9 in YPL-001 groups versus placebo group.
4. To compare blood inflammatory markers (total and differential cell counts as absolute and percentage for neutrophils, monocytes, eosinophils and lymphocytes) and concentrations of CRP, fibrinogen, TNF- α , IL-1 β , IL-4, IL-5, IL-6, IL-8, IL-13, MCP-1, and MMP-9 in YPL-001 groups versus placebo group.
5. To compare spirometric functions (FEV₁, FVC, FEV₁/FVC, and IC) in YPL-001 groups versus placebo group.

6. To compare patient reported outcomes (BDI/TDI, CAT) in YPL-001 groups versus placebo group.
7. To assess verproside and picroside II concentration in plasma and BAL and verproside and picroside II PK in plasma following multiple oral doses administration of two YPL-001 dose levels.

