2.2 Endpoints

Primary Endpoint: The number and severity of treatment-emergent adverse events (TEAEs) following multiple oral doses of YPL-001 or placebo.

Secondary Endpoint: The number of symptom free days and overall symptom burden following multiple oral doses of YPL-001 or placebo, assessed by measuring:

- daily peak expiratory flow (PEF);
- major (e.g., estimated sputum quality (e.g., color, consistency) and quantity) and minor (e.g., cough, wheeze, sore throat, nasal congestion, discharge, and body temperature above 100°F) symptoms of COPD exacerbation;
- dyspnea (using the Modified Borg Dyspnea Scale);
- activity (using the Duke Activity Status Index [DASI]).

Exploratory Endpoints:

1. YPL-001 component levels in epithelial brushings;
2. BAL biomarkers following multiple oral doses of YPL-001 or placebo, measuring:
 - total cell count (cells/mL) of macrophages, lymphocytes, neutrophils, and eosinophils as a percentage of total cells
 - total cell count (cells/mL) of neutrophils, macrophages, lymphocytes, and eosinophils as absolute inflammatory cell numbers
 - concentrations of TNF- α , IL-1 β , IL-4, IL-5, IL-6, IL-8, IL-13, MPO, neutrophil elastase, MCP-1, and MMP-9.
3. Blood biomarkers following multiple oral doses of YPL-001 or placebo, measuring:
 - inflammatory markers (total and differential cell counts as absolute and percentage for neutrophils, monocytes, eosinophils, and lymphocytes)

- concentrations of CRP, fibrinogen, TNF- α , IL-1 β , IL-4, IL-5, IL-6, IL-8, IL-13, MCP-1, and MMP-9.
- 4. Pulmonary function results (spirometry) following multiple oral doses of YPL-001 or placebo.
- 5. Quality of life scores using the BDI/TDI, CAT questionnaires.
- 6. Concentrations and PK of verproside and picroside II in plasma following multiple oral doses of YPL-001.
- 7. Concentrations of verproside and picroside II in BAL following multiple oral doses of YPL-001.

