5.2 Other Treatments

Tiotropium (Spiriva® HandiHaler®) will be supplied as 18 µg capsules for inhalation.

Albuterol will be supplied as 100 µg albuterol base (1 actuation = 100 µg albuterol base) for oral inhalation. Albuterol may be administered via a nebulizer or a metered-dose inhaler.

During the Run-in Period, multiple oral inhalation of tiotropium (Spiriva® HandiHaler®) 18 µg capsule will be administered QD every morning for 14 ± 2 days. Albuterol will be administered on an as needed basis.

In treatments A to C, one tiotropium (Spiriva® HandiHaler®) 18 µg capsule will also be administered QD every morning prior to study drugs administration. Albuterol will be administered on an as needed basis.

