7.1.1.3 Pulmonary Function Biomarkers

Spirometry measures for assessment of the pulmonary function will be taken pre- and post-bronchodilator (albuterol) administration at Screening (baseline), at Check-in, on Days 15 (± 2), 29 (± 2), 43 (± 2), and 55 or 56 (predose) of the Treatment Period, and prior to early termination, if applicable.

Pulmonary function measurements include the following parameters below:

- FEV1;
- FVC;
- FEV1/FVC;
- IC.

Short and long acting β 2-agonist and anticholinergic bronchodilators agents will be withheld approximately 4 and 24 hours, respectively, before each pre-bronchodilator spirometry.

At screening, baseline pre-bronchodilator spirometry will be performed (prior to albuterol administration) for a minimum of 3 times and a maximum of 8 times in order to obtain 3 manoeuvres with FEV1 values within 150 mL of each other, using the manoeuvre with the highest value of FEV1 and FVC as the basis for comparison.

Patients shall receive 4 inhalations of albuterol, (100 μ g/inhalation), for a total dose of 400 μ g via metered-dose inhaler using a spacer. Within approximately 20 to 30 minutes after albuterol administration, the baseline post-bronchodilator spirometry will be performed.

Assessment of FEV1 stability will take place:

1. Prior to Day 1 dosing of the Treatment Period (Check-in measurement): Predose FEV1 is defined as the time-point prior to Day 1 dosing in the Treatment Period and will be performed pre- and post-bronchodilator administration. Predose FEV1 will be compared to the corresponding baseline measurement. If the best FEV1 measurement at predose at Check-in of the Treatment Period has declined by greater than 20% from the best FEV1 at screening, the visit may be rescheduled up to 3 times, at the discretion of the Investigator.
2. Following Day 1 dosing: At all other spirometry time point, measurements will be performed once. If the value shows a difference of greater than 150 mL

decline than the best FEV1 value collected predose at Check-in, up to 3 measures will be performed.

Consideration should be given, if a patient experiences any change in post Day 1 dose FEV1 from the Day 1 predose FEV1 value (measured following dosing with albuterol) equal to or greater than 20 % and should alert the PI to consider whether individual patients should continue to dose.

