Note: Patients following up to Amendment version 5 of the protocol also received a morning dose on Day 56.

Program: /AAXXXX/ECR/sas prg/stsas/tab tab-programname.sas DDMMYYYY HH:MM

Table 14.3.5.9 12-Lead Electrocardiogram Summary and Change From Check-in

Measurement	Day	Statistic	Treatment			Change From Check-in		
			A	B	C	A	B	C
Heart Rate (bpm)	Screen	N	X.XX	X.XX	X.XX			
		Mean	X.XX	X.XX	X.XX			
		SD	X.XX	X.XX	X.XX			
		Median	X.XX	X.XX	X.XX			
		Minimum	X.XX	X.XX	X.XX			
		Maximum	X.XX	X.XX	X.XX			
	Check-in	N	X.XX	X.XX	X.XX			
		Mean	X.XX	X.XX	X.XX			
		SD	X.XX	X.XX	X.XX			
		Median	X.XX	X.XX	X.XX			
		Minimum	X.XX	X.XX	X.XX			
		Maximum	X.XX	X.XX	X.XX			
	29+/-2	N	X.XX	X.XX	X.XX	X.XX	X.XX	X.XX
		Mean	X.XX	X.XX	X.XX	X.XX	X.XX	X.XX
		SD	X.XX	X.XX	X.XX	X.XX	X.XX	X.XX
		Median	X.XX	X.XX	X.XX	X.XX	X.XX	X.XX
		Minimum	X.XX	X.XX	X.XX	X.XX	X.XX	X.XX
		Maximum	X.XX	X.XX	X.XX	X.XX	X.XX	X.XX
	54+/-2	N	X.XX	X.XX	X.XX	X.XX	X.XX	X.XX
		Mean	X.XX	X.XX	X.XX	X.XX	X.XX	X.XX
		SD	X.XX	X.XX	X.XX	X.XX	X.XX	X.XX
		Median	X.XX	X.XX	X.XX	X.XX	X.XX	X.XX
		Minimum	X.XX	X.XX	X.XX	X.XX	X.XX	X.XX
		Maximum	X.XX	X.XX	X.XX	X.XX	X.XX	X.XX

Baseline is Check-in measurement.

Early termination records are excluded from the summary.

QTcB = QT corrected for heart rate using Bazett's Correction

Treatment A: Multiple oral doses of YPL-001 80 mg BID on Days 1 - 55

Treatment B: Multiple oral doses of YPL-001 160 mg BID on Days 1 - 55

Treatment C: Multiple oral doses of placebo BID on Days 1 - 55

Note: Patients following up to Amendment version 5 of the protocol also received a morning dose on Day 56.

<Programmer note: ECG includes heart rate, PR, QRS, QT, and QTcB. >

Program: /AAXXXX/ECR/sas prg/stsas/tabc tab-programname.sas DDMMYYYY HH:MM

Table 14.3.5.10 12-Lead Electrocardiogram Shift From Check-in

Treatment	Day	Predose=Normal			Predose=ANCS			Predose=ACS		
		Postdose			Postdose			Postdose		
		Normal	ANCS	ACS	Normal	ANCS	ACS	Normal	ANCS	ACS
A	29+/-2	X	X	X	X	X	X	X	X	X
	54+/-2	X	X	X	X	X	X	X	X	X
B	29+/-2	X	X	X	X	X	X	X	X	X
	54+/-2	X	X	X	X	X	X	X	X	X
C	29+/-2	X	X	X	X	X	X	X	X	X
	54+/-2	X	X	X	X	X	X	X	X	X

ANCS = Abnormal, Not Clinically Significant, ACS = Abnormal, Clinically Significant
 Baseline is Check-in measurement.

Early termination records are excluded from the summary.

Treatment A: Multiple oral doses of YPL-001 80 mg BID on Days 1 - 55

Treatment B: Multiple oral doses of YPL-001 160 mg BID on Days 1 - 55

Treatment C: Multiple oral doses of placebo BID on Days 1 - 55

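### Bazett is the only QT correction planned, so the descriptive QTc summary can carry heart-rate differences; adding Fridericia is a minor, nearly free improvement

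*SAP*

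**What the plan says.** Section 10.7 gives descriptive statistics by treatment, for results and for change from baseline (Check-in), for "ECG variables (HR, PR, QRS, QT, and QTcB [Bazett's correction"]). The programmer note to Table 14.3.5.9 repeats the list: "ECG includes heart rate, PR, QRS, QT, and QTcB". Its footnote, and the matching one in Appendix 16.2.8.8, define a single correction: "QTcB = QT corrected for heart rate using Bazett's Correction". The Appendix 16.2.8.8 listing also has columns for RR and QT.

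On timing, "Twelve-lead ECGs will be performed at screening, Check-in, Day 29" and Day 55 or 56 (or early termination). Spirometry measures "will be taken pre- and post-bronchodilator (albuterol) administration at Screening (baseline), at Check-in", Days 15, 29 and 43, and Day 55 or 56 (Section 7.1.1.3). Section 5.2 says of Treatments A to C alike: "Albuterol will be administered on an as needed basis".

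The primary objective is "To assess the safety and tolerability of two multiple oral YPL-001 dose levels versus placebo" (Section 2.1). The primary endpoint is "The number and severity of treatment-emergent adverse events (TEAEs) following multiple oral doses of YPL-001 or placebo" (Section 2.2). Section 10 rules out inferential statistics for safety.

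**The concern.** Bazett divides QT by RR to the power 0.5. The result is free of heart rate only if QT really varies with RR to that power. If the true exponent is smaller, a faster rate raises QTcB, and a slower rate lowers it, with no change in repolarisation.

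Heart rate may well vary in this trial. Albuterol is taken as needed, every scheduled ECG visit is also a spirometry visit with albuterol, and arms of 20 leave room for chance imbalance. With one fixed exponent, a reader who sees QTcB move cannot tell from the table how much of the movement depends on that exponent. A rate rise could look like prolongation, and a rate fall could offset a real one. ECG is one of the assessments supporting the primary objective, so a second correction is worth having if it costs almost nothing.

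**Working it through.** The SAP states no QTc threshold, margin or power for ECG, so there is no figure of its own to reproduce. The calculation below is an illustration. The 20 patients per arm come from Section 3; every other input is an assumption.

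**Model.** Let QT = Q60 × RR^b, with RR in seconds (60/HR) and Q60 the QT at 60 bpm. Then:

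- QTcB = QT / RR^0.5 = Q60 × (HR/60)^(0.5 − b)
- QTcF = QT / RR^(1/3) = Q60 × (HR/60)^(1/3 − b)

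The artefact is the change in QTc when only HR changes.

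**Assumed inputs.** Q60 = 400 ms; b from 0.25 to 0.50; HR starting at 70 or 75 bpm; SD of HR 8 to 12 bpm.

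**Worked case.** For b = 1/3 and HR 70 to 75 bpm, QTcB changes by 400 × [(75/60)^(1/6) − (70/60)^(1/6)] = 400 × (1.0379 − 1.0260) = 4.7 ms. QTcF changes by 0.

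**Artefact from 70 bpm (ms).**

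| True exponent b | QTcB, +2 bpm | QTcB, +5 bpm | QTcB, +10 bpm | QTcF, +5 bpm |
|---|---|---|---|---|
| 0.25 | 2.9 | 7.2 | 14.1 | 2.3 |
| 1/3 | 1.9 | 4.7 | 9.2 | 0.0 |
| 0.40 | 1.1 | 2.8 | 5.5 | −1.8 |
| 0.50 | 0.0 | 0.0 | 0.0 | −4.5 |

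The two corrections err about equally where 0.5 − b = b − 1/3, that is b ≈ 0.42. Below that QTcF has the smaller artefact; above it QTcB does.

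**Rate difference needed.** From 75 bpm, a 5 ms artefact in QTcB takes a difference of about 3.7, 5.6 or 9.7 bpm for b = 0.25, 1/3 or 0.40.

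**Chance imbalance.** SE of an arm difference in mean HR = SD × √(2/20).

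| Assumed SD of HR (bpm) | SE (bpm) | Artefact at 1 SE (ms) | Artefact at 1.96 SE (ms) |
|---|---|---|---|
| 8 | 2.53 | 2.3 | 4.5 |
| 10 | 3.16 | 2.9 | 5.5 |
| 12 | 3.79 | 3.4 | 6.6 |

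These are from 75 bpm with b = 1/3. The artefact is roughly proportional to 0.5 − b, so it would be about 1.5 times as large at b = 0.25 and zero at b = 0.50.

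**Can QTcF be recovered from the planned tables?** No. QTcF is a non-linear function of each patient's QT and RR, so its mean, SD and maximum do not follow from summaries of HR and QT. It can be computed patient by patient from the listing.

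**The case against.** A reader might infer that any heart-rate difference produces a false QTc difference, and that this reaches the primary safety result. The documents support neither. The artefact is zero if the exponent is 0.5, and at 2 bpm it is 0 to 2.9 ms over the range above. The primary endpoint is TEAEs. QTcB enters a descriptive table with no test, threshold or decision rule, and the ECG shift table uses normal/abnormal classes that the SAP does not define by QTcB.

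A reader might also infer that albuterol itself separates the arms. It is allowed in all three alike, the trial is randomised and double-blind, and Section 7.1.1.3 withholds short-acting beta-agonists for about 4 hours before each pre-bronchodilator test. An arm difference needs unequal use, a drug effect on rate, or chance. The SAP does not give the order of ECG and albuterol on shared days. That may be in the protocol and is not counted as an omission.

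Large examples are easy to build. A QT of 360 ms at 90 bpm gives QTcB 441 ms and QTcF 412 ms, but that 29 ms is a gap between formulas on one ECG, not an arm difference. Holding QTcF at 410 ms, a rise from 75 to 85 bpm moves QTcB from 425.5 to 434.5 ms. A 10 bpm arm difference would, however, be 2.6 to 4 standard errors under the SDs assumed above.

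Finally, HR and uncorrected QT are tabulated beside QTcB, so a shift in rate is visible, and the SAP applies Bazett consistently. All of this stands, and it limits the severity. It does not supply a second corrected interval: the HR column warns that rate moved but does not show what QTc would be under another exponent.

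**Conclusion.** The point holds as a minor, free improvement. QTcB is the only corrected QT planned, and under assumed exponents of 0.25 to 0.50 a 5 bpm difference from 70 bpm puts 7.2 to 0 ms into it. Chance imbalance with 20 per arm can account for about 2 to 7 ms at exponent 1/3 and an assumed HR SD of 8 to 12 bpm. QTcF is less rate-sensitive only if the exponent is below about 0.42, so it is not free of rate in general. The case is for showing both corrections, not for calling Bazett an error. What is affected is a descriptive summary that supports the primary objective; the TEAE endpoint is untouched.

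**What to change.** Derive QTcF = QT / RR^(1/3) for each ECG from the QT and RR already in Appendix 16.2.8.8, converting RR from milliseconds to seconds first. Add QTcF beside QTcB to the variable list in Section 10.7, to Table 14.3.5.9 (programmer note and footnote) and to Appendix 16.2.8.8. State in Section 10.7 that QTcB and QTcF are to be read together with the change in HR. The cost is one derived variable, one extra table block and one listing column. No new data are needed, and nothing changes for the primary endpoint.

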10.8 Concomitant Medications

Concomitant medications will be coded with the WHO Drug Dictionary 01MAR2015 version and presented in the data listings.

10.9 Physical Examination

Physical examination will occur at screening, Check-in, Day 29, and Day 55 or Day 56 early termination. Abnormal physical examination findings at screening will be reported as medical history. Any clinically significant changes compared to screening will be recorded as an AE.

10.10 Medical History

Medical history will be listed by patient.

11. SUMMARY TABLES AND FIGURES

Summary tables and figures are numbered following the International Conference on Harmonization (ICH) structure but may be renumbered as appropriate during the compilation of the tables and figures for the CSR. Please note that all Symptom Monitoring, PD, PK, PK/PD (if applicable), and Safety summary tables and figures will be generated using SAS® Version 9.3 or higher.

The following are lists of TFLs numbers and titles that will be included within the CSR.

11.1 In-text Summary Tables and Figures

The following is a list of table and figure titles that will be included in the text of the CSR. Tables and figures will be numbered appropriately during compilation of the CSR.

Section 10:

Table 10-1 Disposition Summary by Treatment

Section 11 (Symptom Monitoring, PD, PK, PK/PD (if applicable)):

Note to programmer: the following list of in-text tables and figures may be modified and numbering adjusted.

Symptom Monitoring

Table 11-1 Summary and Change From Baseline of Main Peak Expiratory Flow (PEF) Recorded in the e-Diary Following Multiple Oral YPL-001 Doses of 80 mg and 160 mg and Placebo in COPD Patients

Table 11-2.1 Summary of Sputum Quantity for Symptoms of Chronic Obstructive Pulmonary Disease (COPD) Exacerbation Recorded in the e-Diary Following Multiple Oral YPL-001 Doses of 80 mg and 160 mg and Placebo in COPD Patients

Table 11-2.2 Summary of Sputum Color for Symptoms of Chronic Obstructive Pulmonary Disease (COPD) Exacerbation Recorded in the e-Diary Following Multiple Oral YPL-001 Doses of 80 mg and 160 mg and Placebo in COPD Patients

Table 11-2.3 Summary of Sputum Consistency for Symptoms of Chronic Obstructive Pulmonary Disease (COPD) Exacerbation Recorded in the e-Diary Following Multiple Oral YPL-001 Doses of 80 mg and 160 mg and Placebo in COPD Patients

Table 11-3.1 Categorical Summary of Symptom Score for Symptoms of Chronic Obstructive Pulmonary Disease (COPD) Exacerbation Recorded in the e-Diary Following Multiple Oral YPL-001 Doses of 80 mg and 160 mg and Placebo in COPD Patients

Table 11-3.2 Summary and Change From Baseline of Symptom Severity Score for Symptoms of Chronic Obstructive Pulmonary Disease (COPD) Exacerbation Recorded in the e-Diary Following Multiple Oral YPL-001 Doses of 80 mg and 160 mg and Placebo in COPD Patients

Table 11-4 Summary and Change From Baseline of Modified Borg Dyspnea Scale Recorded in the e-Diary Following Multiple Oral YPL-001 Doses of 80 mg and 160 mg and Placebo in COPD Patients

Table 11-5 Summary and Change From Baseline of Calculated Score from 12-Item Questionnaire of Duke Activity Status Index (DASI) Recorded in the e-Diary Following Multiple Oral YPL-001 Doses of 80 mg and 160 mg and Placebo in COPD Patients

Pharmacodynamics

Table 11-6 Summary of BAL WBC and Differential Following Multiple Oral YPL-001 Doses of 80 mg and 160 mg and Placebo in COPD Patients – Day 55 or Day 56 (% Change from Baseline)

Table 11-7 Summary of BAL Inflammatory Marker Concentration Changes Following Multiple Oral YPL 001 Doses of 80 mg and 160 mg and

Placebo in COPD Patients – Day 55 or Day 56 (% Change from Baseline)

Table 11-8 Summary and Change From Baseline of Pre-Bronchodilator Spirometric Functions Following Multiple Oral YPL-001 Doses of 80 mg and 160 mg and Placebo in COPD Patients

Table 11-9 Change From Baseline of Combined Focal Score (-9 – +9) from Transition Dyspnea Index (TDI) Following Multiple Oral YPL-001 Doses of 80 mg and 160 mg and Placebo in COPD Patients

Table 11-10 Summary and Change From Baseline of Total Score (0 – 40) from Chronic Obstructive Pulmonary Disease (COPD) Assessment Test (CAT) Following Multiple Oral YPL-001 Doses of 80 mg and 160 mg and Placebo in COPD Patients

Figure 11-1 Mean Blood Inflammatory Cell Counts Versus Time Following Multiple Oral YPL-001 Doses of 80 mg and 160 mg and Placebo in COPD Patients

Note: This will be a multi-panel figure including plots for total inflammatory cells, monocyte, lymphocyte, neutrophil, and eosinophil (total of 5 panels).

Figure 11-2 Mean Blood Inflammatory Marker Concentration Changes from Baseline Versus Time Concentrations Following Multiple Oral YPL-001 Doses of 80 mg and 160 mg and Placebo in COPD Patients

Note: This will be a multi-panel figure spreading on 2 pages including plots for CRP, fibrinogen, TNF- α , IL-1 β , IL-4, IL-5, IL-6, IL-8, IL-13, MCP-1, and MMP-9 (total of 11 panels).

Figure 11-3 Mean Spirometric Function Changes in Activity from Baseline Versus Time Following Multiple Oral YPL-001 Doses of 80 mg and 160 mg and Placebo in COPD Patients

Note: This will be a multi-panel figure including plots for FEV1, FVC, FEV1/FVC, and IC pre- and post-bronchodilator change in activity (total of 4 panels).

Pharmacokinetics

Table 11-11 Summary of Plasma Verposide Pharmacokinetic Parameters Following Single Oral YPL-001 Doses of 80 mg and 160 mg in COPD Patients – Day 1

Table 11-12 Summary of Plasma Verposide Pharmacokinetic Parameters Following Multiple Oral YPL-001 Doses of 80 mg and 160 mg in COPD Patients – Day 54 (± 1) or Day 56

Table 11-13 Statistical Comparisons of Dose-Normalized Plasma Verposide Pharmacokinetic Parameters Following Multiple Oral YPL-001 Doses of 160 mg Versus Multiple Oral YPL-001 Doses of 80 mg in COPD Patients – Day 54 (± 1) or Day 56 (Treatment B Versus Treatment A)

Table 11-14 Epithelial Brushing Verproside Concentrations Following Multiple Oral YPL-001 Doses of 80 mg and 160 mg in COPD Patients – Baseline and Day 55 or Day 56 (Treatments A and B)

Table 11-15 Summary of Plasma Picroside II Pharmacokinetic Parameters Following Single Oral YPL-001 Doses of 80 mg and 160 mg in COPD Patients – Day 1

Table 11-16 Summary of Plasma Picroside II Pharmacokinetic Parameters Following Multiple Oral YPL-001 Doses of 80 mg and 160 mg in COPD Patients – Day 54 (\pm 1) or Day 56

Table 11-17 Statistical Comparisons of Dose-Normalized Plasma Picroside II Pharmacokinetic Parameters Following Multiple Oral YPL-001 Doses of 160 mg Versus Multiple Oral YPL-001 Doses of 80 mg in COPD Patients – Day 54 (\pm 1) or Day 56 (Treatment B Versus Treatment A)

Table 11-18 Epithelial Brushing Picroside II Concentrations Following Multiple Oral YPL-001 Doses of 80 mg and 160 mg in COPD Patients – Baseline and Day 55 or Day 56 (Treatments A and B)

Figure 11-4 Arithmetic Mean Plasma Verproside Concentrations Versus Time Following Single and Multiple Oral YPL-001 Doses of 80 mg and 160 mg in COPD Patients - Day 1 and 54 (\pm 1) or Day 56 (Linear Scale)

Figure 11-5 Arithmetic Mean Plasma Verproside Concentrations Versus Time Following Single and Multiple Oral YPL-001 Doses of 80 mg and 160 mg in COPD Patients - Day 1 and 54 (\pm 1) or Day 56 (Semi-Log Scale)

Figure 11-6 Arithmetic Mean (SD) Plasma Verproside Trough (Predose) Concentrations Versus Time Following Multiple Oral YPL-001 Doses of 80 mg and 160 mg in COPD Patients (Linear Scale)

Figure 11-7 Arithmetic Mean Plasma Picroside II Concentrations Versus Time Following Single and Multiple Oral YPL-001 Doses of 80 mg and 160 mg in COPD Patients - Day 1 and 54 (\pm 1) or Day 56 (Linear Scale)

Figure 11-8 Arithmetic Mean Plasma Picroside II Concentrations Versus Time Following Single and Multiple Oral YPL-001 Doses of 80 mg and 160 mg in COPD Patients - Day 1 and 54 (\pm 1) or Day 56 (Semi-Log Scale)

Figure 11-9 Arithmetic Mean (SD) Plasma Picroside II Trough (Predose) Concentrations Versus Time Following Multiple Oral YPL-001 Doses of 80 mg and 160 mg in COPD Patients (Linear Scale)

Section 12 (Safety):

Table 12-1 Incidence of Treatment-Emergent Adverse Events

